## 1.0 TRIAL SUMMARY

FIGURE 1: BLOCK FORMAT TRIAL SUMMARY

|                             |                                                                     |
|-----------------------------|---------------------------------------------------------------------|
| Abbreviated Title           | Kidney cancer treatment: 5-in-a-row IL2 w/ pembrolizumab            |
| Trial Phase                 | Feasibility (phase II)                                              |
| Clinical Indication         | Metastatic kidney cancer                                            |
| Trial Type                  | Treatment                                                           |
| Type of control             | Historical                                                          |
| Route of administration     | IV: pembrolizumab (Keytruda™)
IV: IL-2 (aldesleukin; Proleukin™) |
| Trial Blinding              | None—open label                                                     |
| Treatment Groups            | Single dose level                                                   |
| Number of trial subjects    | 26                                                                  |
| Estimated enrollment period | 4/2017 to 3/2019                                                    |
| Estimated duration of trial | 3 years                                                             |
| Duration of Participation   | 9 months treatment. 1-year landmark evaluation.                     |

Funding supported by: Prometheus Labs, San Diego, CA.

Drug supplied: Pembrolizumab [MK-3475] supplied by Merck.

Aldesleukin IL-2: Commercial supply.

Regulatory Sponsor: Moffitt Cancer Center

Data management: Moffitt Cancer Center

## **Narrative synopsis**

*Medication background:* IL-2 is a cytokine drug and PD-1 antibodies are immunotherapy drugs with demonstrated activity in kidney cancer, including a few patients with complete responses. Whereas IL-2 binds to an activating receptor (CD25/CD122/CD132; IL-2R $\alpha\beta\gamma$ ) on lymphocytes, and has decades of experience in clinical application, PD-1 antibodies such as pembrolizumab bind to and block the function of PD-1 receptors (CD 279) that decrease activation that would be prevented by ligation of PD-L1 (CD274; B7-H1), and are relative new entrants in oncologic therapeutics. The downstream physiologic events for either medication are well-studied, but complex, with changes of behavior of multiple, and varying, subsets of lymphocytes that may ultimately mediate the therapeutic effect. There is not a particular specific pathway that can be claimed to be a simple mechanism of action, for either. Similarly prediction of for whom there will be a major therapeutic response remains an inexact process, despite significant efforts in the separate experiences. While IL-2 therapy (referring to Proleukin™ prescribing information) requires a controlled, experienced setting for safe administration, pembrolizumab is a relatively simpler infusion process (as described on the Keytruda™ prescribing information), with outpatient infusions typically with no immediate complications. Immune-related or cytokine-related side effects of the two medicines also differ as far as kinetics. Typically (even when severe), IL-2 side effect subside within days of cessation of administration; immune activation events of PD-1 directed immunotherapy may require active therapy with corticosteroids or other immunosuppressants, for weeks or more.

*Outcome goals background:* As a fundamental goal of anticancer therapy, the durable, complete response remains a gold standard. In this prospective protocol concurrent, coordinated use of these two immunotherapies will be administered to patients in a prospective series, in the setting of an experienced IL-2 center. The use of a single-arm trial format will accommodate the key scientific developmental question of feasibility. An estimate of response completeness and durability will also be calculated. Response and side effect experiences can be tabulated, but without the scale of a trial with a randomized treatment assignment, cross trial comparisons remain mathematically limited.

*Treatment plan:* Patients with clear cell kidney cancer will be included; the extent of recent prior pretreatment will be restricted, consistent with the usual use of IL-2 (initial therapy) or with the indication of a related medication (nivolumab: after anti-angiogenic therapy). There are four blocks of 9 weeks (3 pembrolizumab infusions each, and interval radiologic and clinical disease assessment); the second and third blocks have concurrent administration of IL-2, with 20 planned doses divided into four courses of 5 doses each; and then the protocol treatment is discontinued which will address unmaintained durability for responses. This IL-2 schedule differs from the Proleukin™ prescribing information in which two courses of 14 doses each are used, by having more planned breaks, but the cumulative planned dose (20 IL-2 doses/block) is comparable to the typical delivered dose of the 14-dose plan. In the prior institutional experience with the 5-in-a-row IL-2 treatment as monotherapy, the 5 year OS was 65% among 20 kidney cancer subjects.

## **2.1 TRIAL DESIGN**

### **2.2 Trial Design**

Overall schedule plan: The treatment is organized into blocks of 9 weeks, with pembrolizumab treatment planned for weeks 1, 4 and 7. On the second and third blocks, interleukin-2 is added, for 5 doses at a time, one dose every 8 hours, on a weekly schedule on the two weeks after the week 1 and the week 4 pembrolizumab doses. This works out to a plan of 20 doses per 9 week block. The fourth block is again pembrolizumab monotherapy, as was the first. If delays occur prior to the 2nd or 3rd block, up to one additional 3 week (one dose) pembrolizumab dose may be added, to keep the overall pattern, within the second and third blocks. If a complete response is identified (including after block 1), then pembrolizumab can be continued as specified to the end of block 4, or stopped sooner after at least 2 interval scans showing complete response, at the discretion of the treating physician or the study PI. The protocol specified treatment finishes after the end of the 4th block. This will typically be 36 weeks after start, but extra 3-week cycles of pembrolizumab are allowed, if needed to maintain the overall schedule, so duration of treatment may turn out to be a month or two longer.

There is no dose escalation portion: The dose and schedule of IL-2 is fixed, 600,000 IU/kg/dose, with a cap of 66 mIU/dose. Doses may be omitted for safety. The dose of pembrolizumab is fixed, flat dose 200 mg/dose.

Safety monitoring: Sequential boundaries will be used to monitor dose-limiting toxicity rate. There is a detailed plan in section 8.5

### **2.3 Pembrolizumab dose plan**

Note: The definitions of immune related adverse events (irAE) are 7.1.2.1.

The dose of pembrolizumab is 200 mg/dose. This is an immunotherapy for which a sharp dose-response relationship of the irAEs to the pembrolizumab is not anticipated.

The pembrolizumab dose of subjects already on treatment may be delayed or omitted for safety reasons.

[figure not shown]
## **2.4 Trial Diagrams**

### **2.4.1 Treatment intervals**

*Key features:* In the absence of schedule adjustments, all treatment starts (pembrolizumab or IL-2 admission) could be the same day of the week.

[figure not shown]
At least 5 days between the end of IL-2 admission and next pembrolizumab infusion gives time for resolution of IL-2 side effects before the irAE assessment before the next pembrolizumab dose.

FIGURE 2: DOSE DAYS INTERVAL DIAGRAM

## 2.4.2 Infusion intervals

FIGURE 3: INFUSION TIMES AND INTERVALS SUMMARY

\* Usual standard of care nursing assessment on IL-2 ward.

### 3.1 OBJECTIVES & HYPOTHESES

#### 3.2 Primary Objective & Hypothesis

(1) **Objective-Efficacy portion:** Estimate the frequencies of disease response so as to be a basis to commit to more development of this schedule. Note that this is framed broadly, with the understanding that the decision to commit to further development of the schedule includes a variety of feasibility endpoints.

The ORR will be defined as the CR + PR patients, with confirmation of the response status (numerator), among those ever treated (denominator). **Hypothesis:** For the efficacy portion  $H_0$ : ORR is  $<20\%$  and  $H_A$ : ORR is  $>45\%$ . Thus, a 45% ORR (CR + PR) would be considered of definite interest for further development, contingent on the feasibility assessment as well, as part of the decision. With a Simon 2-stage design, 24 evaluable patients are needed.

**Objective –Safety portion:** The co-primary endpoint of adverse event and serious adverse event tabulation comprises a critical portion of the ultimate assessment of feasibility for moving forward with additional and directly comparative trials using this regimen. There are known frequencies of these (referencing the respective monotherapy prescribing information documents) for which this tabulation can be compared. The relatively small sample size of this series versus those series typically would prevent specific hypothesis testing.

#### 3.3 Secondary Objectives & Hypotheses

(1) **Objective:** ORR for patients getting at least 4 doses of pembrolizumab and one dose of IL-2:

(2) Objective: ORR for, and for patients completing at least 6 doses of pembrolizumab and at least 20 doses of IL-2 (designated as “completing at least half of the treatment per-protocol”).

(3) **Objective:** This is an exploratory safety objective: OS will be not demonstrably inferior to contemporary subjects with matched clinical risk features from PROCLAIM database observed OS (using  $p \geq .05$ )

**Hypothesis:**  $H_0$ : OS[1-year] is more than 20% lower than matched controls

$H_A$ : ORR is same or better (using  $p \geq .05$ )

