#### 4.4.4 Rationale for Endpoints

##### 4.4.4.1 Efficacy & Dose Delivery Endpoints

This is primarily a feasibility study. There is a formal safety format, because this is the initial human clinical experience with the two drugs together on this schedule. Feasibility for further development encompasses two issues:

The first is the response rate of the disease. The trial design is a small, single arm design and would not be definitive for a registration or practice changing decision. Thus, the response rate will not be determined with high precision. Since differentiation of CR and very-good PR, by radiologic criteria, can be an issue for which determinations are ambiguous, and since the CR+PR (major response rate) is the typical metric for a new combination evaluation, the CR will be assessed, but the CR+ PR will be used as the primary outcome measure. Another key metric is overall survival or progression free survival; these have been shown to be typically better among patients who have been treated with IL-2 than those (non-randomly assigned) to not get IL-2, but require much longer time frame for follow up, and again do not lend themselves to definitive analysis in the present single arm trial.

The second is the dose delivery. The proposition of this trial is that each of the drugs will contribute, and that this schedule is relevant. That can only be part of the logical conclusion if patients actually get the treatments as planned. If a very low dose delivery is achieved, and a high response rate is observed – that is generally good, but favors planning to use a different schedule in further testing. If a high dose delivery is achieved, but the response rate is unfavorable, that technically meets feasibility, but does not favor planning to continue to use this schedule. If the overall response rate (primary endpoint) of the trial is met and the dose delivery is relatively good, that would favor continued development of this dose and schedule for these drugs, for these type of patients.

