### 5.5 Stratification

There is no stratification on this trial, as there is only one arm..

Risk features are tabulated for accommodation of retrospective comparisons of outcomes.

These may include:

1. Age
2. Time from diagnosis to treatment
3. Sites of metastatic disease
4. Absolute neutrophil count
5. Hemoglobin
6. Platelet count

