#### 8.4 Planned primary reporting analyses

Analysis: Overall response rate ORR is defined with confirmation of the response status CR or PR among the combination treatment population patients; the binomial estimate and its one-sided 95% confidence interval will be reported.

Analysis: Overall survival (OS) of ITT patients counting from the eligible date to death from any cause, or censored on end of known follow up, either within this study or in the PROCLAIM registry.

Analysis: Progression-free survival (PFS) of ITT patients from the confirmed eligible date to the first occurrence of disease progression or death, from any cause, or lost to follow up, whichever is earliest; or censored at last follow-up during study.

Kaplan-Meier method will be used for OS as well as PFS analysis.

The Simon minimax two-stage design (Simon, 1989) with a 10% type I error and 90% power will be used to test the null hypothesis that overall response rate (CR+PR)  $\leq 0.20$  versus the alternative hypothesis of overall response rate  $>0.45$ . In the 1st stage, 15 patients will be treated. If 3 or fewer respond, the trial will be terminated. If 4 or more respond, an additional 9 evaluable patients (the “combination treatment population”) will be studied in the 2nd stage (a total of  $n=24$  evaluable patients). If the total number responding is less than or equal to 7, the drug is rejected. This design has an expected sample size of 18 patients with a probability of early termination of 0.65.

The overall total number of patients, counting patients with at least one dose of IL-2 administered, will be up to  $n =26$ . This will accommodate replacement of subjects who are in the intent-to-treat(ITT) population, but not part of the main developmental objective of the study, which is the combination treatment population.

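### Secondary objective (3) accepts survival as no worse than matched controls on p ≥ .05, although its null hypothesis is the 20% deficit, and its alternative names ORR instead of OS

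*Combined protocol and SAP*

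**What the plan says.** Objective (3) in section 3.3 (Secondary Objectives & Hypotheses) is introduced with "This is an exploratory safety objective". Its aim is that "OS will be not demonstrably inferior to contemporary subjects with matched clinical risk features from PROCLAIM database observed OS", with p ≥ .05 as the criterion. The null hypothesis is "OS[1-year] is more than 20% lower than matched controls". The alternative is "ORR is same or better", again with p ≥ .05.

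The analysis sections contain no matching comparison. Section 8.2 plans landmark one-year OS by Kaplan-Meier. Section 8.4 says "Kaplan-Meier method will be used for OS as well as PFS analysis", defines OS in the ITT population from the eligible date, and mentions the PROCLAIM registry only as a source of follow-up for censoring. On matching, section 5.5 says "Risk features are tabulated for accommodation of retrospective comparisons of outcomes" and lists features that may be included.

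Two other places set limits on such comparisons. The narrative synopsis says "cross trial comparisons remain mathematically limited", and section 4.4.4.1 says that OS and PFS "do not lend themselves to definitive analysis in the present single arm trial".

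**The concern.** The null hypothesis is the harmful state, which is the form of a non-inferiority test. Evidence against harm then means rejecting that null with a small p. The plan ties the favourable alternative to a large p, so absence of evidence is read as evidence of no harm. The fewer the patients, the easier the criterion is to meet.

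The alternative also concerns ORR while the null concerns 1-year OS. The two are not complements, and taken literally a survival question could be answered with response data.

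At stake is a sentence in the trial report. It could say that survival is as good as or better than that of matched controls when it is worse by the margin the plan itself sets. This is labelled a safety objective, in what section 4.4.4.1 describes as the first human experience with the two drugs together on this schedule.

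**Working it through.** **No figure to reproduce.** The documents give no power, control survival rate, number of controls, test or sidedness for this objective. They also do not say whether 20% is absolute or relative. The direction of the error follows from the wording alone; its size needs assumptions.

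**Inputs from the documents.** 24 evaluable patients (sections 3.2 and 8.4); up to 26 enrolled (sections 1.0 and 8.4); 15 if the trial stops after stage 1 (section 8.4); margin 20%; criterion p ≥ .05 (section 3.3).

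**Assumptions.** Control 1-year OS of 70, 80 or 90%; 24, 48 or 96 controls; 1-year OS treated as two independent binomial proportions, which ignores matching and censoring. Each probability is an exact sum over all pairs of outcomes.

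**Reading (a): p comes from a test of no difference.** The statistic is z = (p_T − p_C) / √[p(1 − p)(1/n + 1/m)], where p is the pooled proportion, n the number of trial patients and m the number of controls. The criterion is met when p ≥ .05.

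A hand check with n = m = 24, controls at 80% and the trial at 60%:
- The pooled proportion is 0.70 and the standard error is √(0.70 × 0.30 × 2/24) = 0.132.
- Two-sided significance needs an observed difference of at least 1.96 × 0.132 = 0.259, which is larger than the true deficit of 0.20.
- With unpooled standard error √(0.6 × 0.4/24 + 0.8 × 0.2/24) = 0.129, the chance of passing is about Φ[(0.259 − 0.20)/0.129] = Φ(0.46) ≈ 0.68. The exact value is 0.667.

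Exact chance that a true absolute 20-point deficit passes, n = 24:

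| Control OS | Controls | Two-sided | One-sided |
|---|---|---|---|
| 70% | 24 | 0.690 | 0.578 |
| 70% | 96 | 0.540 | 0.419 |
| 80% | 24 | 0.667 | 0.556 |
| 80% | 48 | 0.538 | 0.427 |
| 80% | 96 | 0.449 | 0.353 |
| 90% | 24 | 0.569 | 0.445 |
| 90% | 96 | 0.310 | 0.226 |

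Ranges over the same grid for other settings:

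| Setting | Two-sided | One-sided |
|---|---|---|
| n = 26, absolute 20 points | 0.29–0.68 | 0.22–0.57 |
| n = 15, absolute 20 points | 0.46–0.75 | 0.36–0.65 |
| n = 24, relative 20% | 0.38–0.82 | 0.29–0.74 |

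**Reading (b): p comes from a test of the stated null hypothesis.** The statistic is z = (p_T − p_C + 0.20) / √[p_T(1 − p_T)/n + p_C(1 − p_C)/m], and a large p means the deficit was not rejected. With n = 24:
- a deficit exactly at the margin passes 0.92 to 0.95 of the time;
- with controls at 80%, a 30-point deficit passes 0.99 of the time;
- with controls at 80%, equal survival passes only 0.45 of the time (24 controls) or 0.32 (96 controls).

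Under this reading the rule is inverted: worse survival passes more often.

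**Confidence-bound rule for comparison.** Claim non-inferiority only if the one-sided 95% lower bound for p_T − p_C exceeds −0.20. With n = 24 and a Wald bound, a true deficit at the margin is wrongly cleared 0.052 to 0.080 of the time. With truly equal OS of 80%, the claim succeeds 0.550, 0.639 or 0.683 of the time with 24, 48 or 96 controls.

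**The case against.** The strongest reply is that little depends on this objective. It is labelled exploratory, section 4.4.4.1 and the synopsis already limit what survival can show, the go/no-go decision rests on ORR, and accrual suspension rests on the toxicity boundary. Section 8 plans no PROCLAIM test at all, so the analysis as written would not produce the p-value. All of this stands and limits the consequence. It does not make the rule correct. The objective sits among the secondary objectives with a formal null, alternative and criterion, so the test could be run ad hoc, and the caveats elsewhere argue for removing the criterion.

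It is also fair that failing to demonstrate inferiority is literally what a non-significant difference test shows, so the objective's opening sentence can be defended. The overreach is in the alternative, which asserts equality or superiority.

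Reading (b) is unlikely to be what anyone would apply; it shows that the text is incoherent and does not give a realistic error rate. Reading (a) is the realistic one, and its range is wide because the plan leaves its inputs open.

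The ORR wording is probably a drafting slip, but nothing in the documents corrects it, and correcting it would leave the p ≥ .05 rule in place. The missing matching and test details are a separate omission. Section 8.4 does name ITT as the OS population, so only its use for the PROCLAIM comparison remains to be confirmed. Using 26 in place of 24 patients changes the two-sided range only from 0.31–0.69 to 0.29–0.68.

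**Conclusion.** The point holds: the criterion is wrong as written. A favourable survival conclusion is attached to a non-significant p-value although the null hypothesis is the deficit, and the alternative names the wrong endpoint. These two defects rest on the text alone.

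Under reading (a), with 24 patients and an absolute 20-point deficit, the chance of a falsely reassuring result is 0.31 to 0.69 two-sided or 0.23 to 0.58 one-sided. These figures depend on the assumed control OS of 70 to 90%, 24 to 96 controls, and independent proportions without censoring. Other assumptions would change the size of the error but not its existence. The change should be made, but the matter is confined to one exploratory statement and does not touch the trial's decision rules.

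**What to change.** In section 3.3, objective (3): replace ORR with OS in the alternative, delete the p ≥ .05 criterion in both places, and have the sponsor state whether the 20% margin is absolute or relative.

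In section 8.4: add a short paragraph that reports the difference in 1-year Kaplan-Meier OS (trial minus matched PROCLAIM controls) with its confidence interval, descriptively. It should confirm that the ITT set is used and fix the matching features and the number of controls. If a non-inferiority statement is kept, allow it only when the one-sided 95% lower bound lies above the stated margin, and otherwise call the result inconclusive. Dropping the statement and reporting descriptively would also resolve the defect.

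The cost is wording only; sample size and conduct do not change. The price is that a non-inferiority statement becomes harder to earn. With an absolute 20-point margin, a Wald bound and truly equal survival, its chance with 24 to 96 controls is:
- 0.55 to 0.68 with 24 patients and 80% OS;
- 0.46 to 0.60 with 24 patients and 70% OS;
- 0.48 to 0.57 with 15 patients and 80% OS.

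A simple Wald bound is also somewhat liberal at these sizes. Its error at the margin reaches 0.080 with 24 patients and 0.094 with 15, so the method for the bound should be chosen with that in mind.

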### 3.4 Exploratory Objectives

These objectives are expected to be developed as part of testing in parallel with testing of patients on other trials. While the specific conceptual goals are outlined here, the specific tests are not prespecified.

(1) **Objective:** Exploratory analyses dividing retrospectively designated best responders versus remaining patients with respect to a variety of cell subsets, for example: DC:MDSC ratio; CD4+ : CD4: FoxP3+ ratio. CD8+ : NK cell ratio.

**Hypothesis:** Pretreatment leukocyte characteristics will predict response

(2) **Objective:** Exploratory analyses dividing retrospectively designated best responders versus remaining patients with respect to sets of immune related proteins assayed by Nanostring™ testing of tumor specimens for gene sets that have been proposed to be related to the chance of anticancer immune response.

**Hypothesis:** The good-responder patients will have an overall pattern consistent with those seen patients with other diagnoses who had had good response after other PD-1 treatment. For example, better responses if there is tissue PD-L1 expression > 5%, or interferon-gamma related gene expression.

(3) **Objective:** Exploratory analyses of selected serum proteins to analyze for markers of immune response.

**Hypothesis:** The good-responder patients will have an overall pattern consistent with those seen patients with other diagnoses who had had good response after other PD-1 treatment.

